4.2 Data Collection

The data sources for study participants and the pool of potential controls are not all the same because we don't enroll matched controls in this study. To make sure both groups are symptomatic, we will use Optum electronic medical record (EMR) data to select symptomatic COVID-19 cases as candidates of control, while this information for study participants comes from ProtectWell symptoms data. We summarize the data sources for study participants and matched controls in Table 1.

For enrolled participants, tracked data collection begins from first report of symptoms via ProtectWell. The data collection timepoints are:

1. First report of symptoms
2. COVID-19 test result (positive – moves forward; negative – resets the experience)
3. Date of receipt of Bamlanivimab (LY3819253) via infusion (Day 1)
4. Day 1 infusion (pre, during, post) collection of CRF data (participant vitals/health information and any events experienced)
5. Day 1 post-infusion baseline wellness check through Day 28 final wellness check
6. Any point during Day 1 post-infusion baseline through Day 28 where wellness check indicates participant is feeling worse
7. Point from participant marking feeling worse through action taken (live daily check-in via clinical support, recommendation to seek medical care and/or requiring hospitalization)

Regarding the timeline, the overall duration for enrolled participants is up to 6 months with symptom tracking only. Once an enrolled participant becomes a study participant after reporting symptoms, it is up to 38 days (28 days of active participation after receipt of infusion on Day 1 and up to 10 days from report of symptoms to receive infusion). For matched controls, the active insurance coverage after date of symptoms onset should be up to 38 days. We require matched controls to remain enrolled in utilized data sources to assure data availability. Similar to enrolled participants, matched controls may die after the synthetic date of treatment.

Commented [WWY1]: Would suggest to add A figure to illustrate study design, including screening and treatment time point and assessment period

Commented [JAT2R1]: Thanks for the suggestion. I added a sentence directing the audience to Figures 2 and 3 on the screening process and timeline.

Table 1. Main data sources of study participants and the potential pool of controls.

Study population	Data name	Data description

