Study participants	Optum infusion pharmacy data	Day 1 at-home infusion will collect vitals and other essential data pre, during and post-infusion using an established case report form (CRF) to collect any events experienced during and post-infusion related to Bamlanivimab (LY3819253)
	ProtectWell data	during symptom tracking – status of what was selected per daily check-in, first trigger point of noting experiencing symptoms, if COVID-19 positive and received infusion – Day 1-28 wellness tracking (in numeric 1-10 ratings)
	UHC claims data (UHC members only)	data including demographic characteristics (e.g., age, gender, race) and existing comorbidities (e.g., congestive heart failure, diabetes, chronic kidney disease)
	Blended Census Reporting Tool (BCRT) data (UHC members only)	real-time inpatient admission data including ICD-10 diagnosis codes, discharge status, COVID test status reviewed by UHC's clinical team; will be used as complementary to Optum infusion pharmacy data for COVID hospitalizations
	Clinical Data Services Management (CDSM) data (UHC members only)	SARS-CoV-2 lab testing data from reporting health systems, clinics, and third-party labs; will be used as complementary to Optum infusion pharmacy data for COVID tests
Potential pool of controls	Optum EMR data	primary source to confirm for presence of symptoms during COVID+ test of a matched individual (analogous to the symptoms collected as part of ProtectWell data for study participants); will also be used for COVID test status and COVID hospitalization of all potential controls, and for demographic characteristics, existing comorbidities, COVID test status and COVID hospitalization of potential non-UHC controls.
	UHC claims data (UHC members only)	data including demographic characteristics (e.g., age, gender, race) and existing comorbidities (e.g., congestive heart failure, diabetes, chronic kidney disease)
	Blended Census Reporting Tool (BCRT) data	real-time inpatient admission data including ICD-10 diagnosis codes, discharge status, COVID test

LY3819253

(UHC members only)	status reviewed by UHC's clinical team; this dataset does not include symptom information during COVID test, hence it will be only used as a potential sensitivity analysis data source

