4.5 Endpoints

The following definitions of endpoints hold for all analyses described in this statistical analysis plan. For study participants, we define the study endpoint as 28 days after date of the Bamlanivimab infusion. This holds for both outcomes of COVID-related hospitalization with or without time consideration (i.e., no censoring vs censoring at Day 28). For example, if a study participant hasn't been hospitalized due to COVID-19 within 28 days after COVID-19 diagnosis, we'll treat the binary response of COVID-19 hospitalization as 0 without time consideration. However, with time consideration, it becomes right-censored since this participant may be hospitalized 29 or more days after COVID-19 diagnosis and our observation period is 28 days after COVID-19 diagnosis. More details are described in Section 5.8.1.3. For the pool of potential controls, we define the study endpoint as 28 days after a synthetic date of treatment. We will randomly select a number from the distribution of number of days after date of symptoms onset in study participants to identify an index date with which to define 28 days post infusion where we will monitor claims and EMR data for hospitalizations and mortality.

Commented [WWY14]: Should be the pool of controls which was before PS matching.

Figure 3 illustrates the timeline for study participants and controls to ensure alignment on an index date for symptoms onset and the follow-up period. Since the control group will not have an infusion date associated with them, we will randomly select a number from the distribution of number of days after date of symptoms onset in study participants to identify an index date with which to define 28 days post infusion where we will monitor claims and EMR data for hospitalizations and mortality.

[figure not shown]

Figure 3. Illustration of the timeline for study participants and controls.

For patients who do not experience a COVID-19 related hospitalization by Day 28 following the date of infusion or synthetic treatment, a censoring date is defined as the earliest of 28 days following the date of treatment, or for study participants, the early discontinuation date due to lost to follow-up.

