In the short term, we will use Optum infusion pharmacy data and BCRT data to identify hospitalization among the treatment group; and we will use UHC claims data and Optum EMR data for inpatient records for identification of COVID-related hospitalizations among the control group. We will evaluate treatment effects based on a two-sided test with a level of 0.05 for all efficacy analyses, and provide 95% confidence intervals for the odds ratio/hazard ratio.

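### SAP 5.8.1.3 identifies the primary outcome from different data sources in treated patients and controls, with no common COVID-admission rule or run-out

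*SAP*

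**What the plan says.** SAP 5.8.1.3 assigns outcome sources by arm. For treated patients: "In the short term, we will use Optum infusion pharmacy data and BCRT data to identify hospitalization among the treatment group". For controls: "we will use UHC claims data and Optum EMR data for inpatient records for identification of COVID-related hospitalizations among the control group". SAP 4.2 acknowledges that "The data sources for study participants and the pool of potential controls are not all the same", because controls are not enrolled, but gives no rule for making outcomes comparable.

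Other sections bear on the same question:

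- **SAP 4.2, Table 1.** In treated patients BCRT "will be used as complementary to Optum infusion pharmacy data for COVID hospitalizations". For controls, Optum EMR "will also be used for COVID test status and COVID hospitalization of all potential controls", while of BCRT it says "this dataset does not include symptom information during COVID test, hence it will be only used as a potential sensitivity analysis data source". UHC claims are described in both groups only as a source of demographics and comorbidities.
- **SAP 4.5.** For controls, "we will monitor claims and EMR data for hospitalizations and mortality". A participant with no observed COVID admission in the 28-day window is scored zero: the SAP will "treat the binary response of COVID-19 hospitalization as 0 without time consideration".
- **SAP 4.7, Phase II.A.** The table is broken in the extracted text. It appears to list BCRT for participants and Optum EMR or BCRT for controls.
- **SAP 5.4.** The disposition rule accepts claims, EMR or infusion pharmacy data as outcome data for participants and does not name BCRT.
- **Protocol 6.5.2.** Short-term outcomes in treated patients come from patient reports and BCRT. In the long term, inpatient claims serve as a consistency check and as the way to identify control hospitalizations.
- **SAP 5.14.** Changes to protocol-planned analyses are given as NA.

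**The concern.** Propensity matching balances baseline covariates. It cannot balance the chance that an admission is found, or that it is labelled COVID-related. With a binary endpoint, a missed admission becomes 0 and a non-COVID admission labelled as COVID becomes 1. If either error differs by arm, the estimated effect moves even when the drug does nothing. The error does not shrink with sample size, so a larger study only makes a spurious difference more likely to reach significance.

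The reason given for limiting BCRT in controls, its lack of symptom data, bears on choosing symptomatic controls. It does not bear on seeing their admissions afterwards. SAP 5.8.3 treats measurement error as random and negligible. Nothing supports that when the source is set by arm.

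**Working it through.** **1. Do the sections settle on a common source?**

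| Section | Treated | Controls |
|---|---|---|
| SAP 5.8.1.3 text | infusion pharmacy, BCRT | UHC claims, Optum EMR |
| SAP 5.8.1.3 table | five sources pooled, no split by arm | same pooled list |
| SAP 4.2 Table 1 | infusion pharmacy, BCRT as complement | Optum EMR; BCRT for sensitivity only |
| SAP 4.5 | not stated | claims, EMR |
| SAP 4.7 (as extracted) | BCRT | Optum EMR or BCRT |
| SAP 5.4 (disposition only) | claims, EMR or infusion pharmacy | not applicable |
| Protocol 6.5.2 | patient report, BCRT; later claims | claims |

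They do not. Within the 5.8.1.3 text the lists are disjoint. SAP 4.7 would allow BCRT in both arms, but that conflicts with 4.2 and 5.8.1.3 and sets no hierarchy.

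**2. Is there a code rule or run-out?** SAP 4.7 collects primary, secondary and tertiary diagnosis codes without saying which of them count. Appendix 1 lists codes or drug names for tests, Elixhauser conditions and immunosuppressants only. SAP 5.13 triggers the primary analysis when Day 28 data exist for the first 1,000 participants and sets no run-out for controls. Claims lag is mentioned only for the nursing-facility row of mock Table A4. The analyses in SAP 5.8.2 address unmeasured confounding and matching, not outcome capture.

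**3. The plan's own sample-size statement.** SAP 4.4.2 says 1,000 pairs suffice to detect 15% against 10% with power 0.8 at level 0.05. The two-proportion formula needs 686 per group (726 with continuity correction). At 1,000 per group power is 0.92 (0.91 corrected). The statement holds, with room to spare.

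**4. Illustration of unequal ascertainment.** All capture and false-flag rates here are assumptions.

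For each arm: observed rate = true rate × capture + (1 − true rate) × false-flag rate.

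Rejection probability, with d the control minus treated observed rate, s0 the pooled and s1 the unpooled standard error: Φ((d − 1.96·s0)/s1) + Φ((−d − 1.96·s0)/s1), n = 1,000 per arm.

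Worked case: no drug effect, true rate 10%, capture 85% treated and 95% control. Observed rates are 0.10 × 0.85 = 8.5% and 0.10 × 0.95 = 9.5%, so d = 0.010, and s0 ≈ s1 ≈ 0.0128. Then Φ(−1.18) + Φ(−2.74) = 0.119 + 0.003 = 12.2%. RR = 8.5/9.5 = 0.895.

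| No drug effect, true rate 10% (treated/control) | Observed rates | RR | P(p<0.05) |
|---|---|---|---|
| Capture 90/95 | 9.0 v 9.5% | 0.947 | 6.7% |
| Capture 85/95 | 8.5 v 9.5% | 0.895 | 12.2% |
| Capture 95/95, 1% false flags in controls | 9.5 v 10.4% | 0.913 | 10.3% |
| Capture 95/95, 1% false flags in treated | 10.4 v 9.5% | 1.095 | 10.3% |
| Capture 90/95, 1% false flags in controls | 9.0 v 10.4% | 0.865 | 18.5% |
| Capture 90/95, 1% false flags in treated | 9.9 v 9.5% | 1.042 | about 6% |

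Over true rates of 5% to 15%, the first row ranges from 5.8% to 7.7%, the second from 8.4% to 16.5%, and the third from 15.9% down to 8.4%. Swapping the capture rates gives the same probabilities in the direction of harm (RR 1.056 and 1.118). At the 7,500 target and a true rate of 10%, capture of 90/95 and 85/95 gives 18% and 57%.

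| True 10% v 15% (treated/control capture) | Observed rates | RR | Power |
|---|---|---|---|
| 95/95 | 9.5 v 14.25% | 0.667 | 91% |
| 95/90 | 9.5 v 13.5% | 0.704 | 80% |
| 95/85 | 9.5 v 12.75% | 0.745 | 64% |
| 90/95 | 9.0 v 14.25% | 0.632 | 96% |

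These figures treat the arms as unpaired, as the SAP's reported sample sizes do. A McNemar simulation with independent pairs (200,000 runs) agrees: 6.6%, 12.1% and 10.2% for the first three null rows, and power of 91%, 80% and 64% for the first three power rows. The documents give no within-pair correlation.

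**The case against.** The best defence is that the 5.8.1.3 sentence describes only a short-term step. Protocol section 2 builds long-term ascertainment from medical records and claims into the primary objective, Protocol 6.5.2 uses inpatient claims for both arms, and SAP 5.14 reports no change. On that reading the claims step still stands. But the SAP does not state it: the objective in SAP 3.1 and the text of 5.8.1.3 both omit it, and nothing says which ascertainment is primary. An analyst following 5.8.1.3 would use different sources by arm.

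There are also partial definitions. SAP 5.8.1.1 counts hospitalization within 38 days of a positive test, but for the risk-factor model only. BCRT is described as reviewed by a clinical team, but that is no rule for the control sources. The move from patient-reported to infusion pharmacy data may be partly relabelling, since a post-infusion form collects clinical information. If so, the SAP should say it.

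Two points stand. Different source names do not prove different capture, and every accuracy figure above is assumed. And the phrase about no shared source is true of the 5.8.1.3 text, not of the whole SAP, because 4.7 appears to allow BCRT in both arms.

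**Conclusion.** The concern holds and should be fixed before outcome data are accessed. As written, SAP 5.8.1.3 makes ascertainment of the primary outcome depend on arm. No section supplies a common source, a code rule or a run-out, and the protocol's claims check in treated patients is missing without an entry in 5.14. Confidence is high on the text. The size of the bias cannot be fixed from the documents: it may favour either arm, and errors may cancel. Under the assumed accuracies, modest differences move the false-positive rate at 1,000 pairs from 5% to somewhere between about 6% and 18% at a true rate of 10%. A 10-point shortfall in control capture cuts power from 91% to 64% in the SAP's own case.

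**What to change.** In SAP 5.8.1.3, define the primary endpoint for UHC members (the analysis populations of SAP 5.1.1) by one algorithm in both arms:

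- the same source or source hierarchy, chosen from inpatient claims and BCRT once inpatient coverage is confirmed in both arms;
- the same COVID diagnosis-code and position rule, listed in Appendix 1;
- the same run-out before the data cut.

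Use sources that exist in one arm only (infusion pharmacy data, self-report) in sensitivity analyses, and add a simple bias analysis that varies capture and false flags by arm. Restore the protocol's claims check in treated patients, or record its removal in 5.14. Record the change of short-term source there too, and any reduced role for self-report, which Protocol section 2 names in the primary objective. Reconcile SAP 4.2, 4.5, 4.7, 5.4 and 5.8.1.3, and delete the statement in 5.8.3 that measurement error is negligible.

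The cost is SAP wording, one code list, a coverage check and, if claims are used, a wait for run-out. Dropping arm-specific sources may reduce the number of captured events. The handling of non-UHC matches, on which SAP 5.1.1 conflicts with 4.4.2 and 5.8.1.2, is a separate matter that this change does not settle.

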5.8.2 Sensitivity Analyses

The validity of all the above analyses relies on the assumption of 'no unmeasured confounding'. That is, the identification of average treatment effects in observational studies is achieved by assuming that the correct set of confounders has been measured and properly included in the relevant models. Thus, sensitivity analysis for the potential impact of unmeasured confounding is important as the assumption of no unmeasured confounding cannot be completely verified. In this study, potential unmeasured confounders include the frequency of interaction with clinicians (e.g., doctors or nurses), viral load (e.g., cycle threshold value from polymerase chain reaction tests), COVID-19 variants (e.g., B.1.1.7 and B.1.351 first identified in the United Kingdom and South Africa, respectively), lifestyle patterns (e.g., activity level or diet pattern), psychosocial factors (e.g., a patient's psychological reaction when facing COVID-19 and its interaction with the disease progression, or if a patient has the support network such as family and friends), etc.

Assuming it is not possible to obtain information on specific unmeasured confounders, plausibility/one-number summary methods, such as the E-value, may be performed as an initial assessment of the robustness of the primary analysis findings to the potential for unmeasured confounding. Specifically, the E-value (VanderWeele, 2017) and the proportion of unmeasured confounding (Bonvini, 2020) may be used to evaluate the robustness of the primary objective in our study (i.e., the difference in COVID-19 hospitalization during Days 1 to 28 analysis between matched study participants and matched controls).

The E-value is defined as "the minimum strength of association, on the risk ratio scale, that an unmeasured confounder would need to have with both the treatment and the outcome to fully explain away a specific treatment-outcome association, conditional on the measured covariates." E-values can be based on the adjusted treatment effect estimate or the confidence limit endpoint of interest.

Secondly, the proportion of unmeasured confounding is a method built upon a mixture model for confounding. The authors conceptualize that an unknown fraction (ε) of the units in the sample is arbitrarily confounded while the rest is not. This framework yields the one-number summary of a study's robustness (i.e., the proportion of unmeasured confounding): the minimum proportion of confounded units such that bounds on the average treatment effect contain zero. The proportion

Commented [XM41]: What's the possible random variable?

Commented [JAT42R41]: Region or state of residence.

Commented [XM43]: Please specify

Commented [XM44]: Describe in detail

Commented [JAT45R44]: I'm not sure what details are desired here. This sentence is for selection of Cox PH and AFT models, and the previous sentence mentions we'll check Schoenfeld residuals for the proportionality assumption of the Cox model.

Commented [XM46]: Would add a paragraph "Treatment effects will be evaluated based on an two-sided significance level of 0.05 for all efficacy analyses. Ninety-five percent confidence intervals (CIs) for the OR/HR will be provided."

Commented [WWY47]: Suggest to add double score matching or prognostic score matching (PrSM) as sensitivity analyses

Commented [JAT48R47]: Added, please see below.

of unmeasured confounding ε ranges from 0 to 1 (i.e., 0% to 100%). In general, a study is more robust when ε is bigger because we need more unmeasured confounding to alter the conclusion of treatment effect, and computation can be done in the sensitivitypuc package in R. Of course, there is no universal threshold to determine if a study is robust enough. This decision making largely depends on subject-matter knowledge to determine if the unmeasured confounding is serious enough to affect the conclusion under the assumption of no unmeasured confounding. Given the results of the initial assessment of unmeasured confounding sensitivity, further analyses may or may not be conducted. For instance, negative control outcomes, treatment comparisons, or perturbation variables are other approaches which could be utilized. See Zhang and colleagues (Zhang, 2018) for a further set of unmeasured confounding sensitivity analysis methods.

In addition, we will use double score matching (Yang, 2020), where matched controls are identified using both propensity and prognostic scores, rather than the propensity score only. We want to emphasize that the model-based matching (i.e., propensity and dual matching) are only applicable for UHC members; we will not have information available for all prognostic factors to calculate model-driven scores for non-UHC members. We will compute the propensity score as described in Section 5.8.1.2. The prognostic score is defined as the predicted outcome under the control group. It is estimated by modeling the COVID-19 related hospitalization using only the pool of potential controls, and then using the model to obtain the prediction of potential outcomes for the treatment group. Aside from the modeling method (logistic regression) described in Section 5.8.1.1, we also consider ensemble-based machine learning models (e.g., gradient boost, random forest, bagging, and support vector machine). We randomly split the historical cohort data (i.e., dataset described in Section 5.8.1.1 iteration 1) data into a training and test set (i.e., 80%-20%) ensuring the same proportion of cases (i.e., the observed number of hospitalization in control group divided by the total number of COVID cases) in each cohort. Next, we develop the models based on the training set, and evaluate their performances on the test set. We repeat the process 100 times, report the average classification metrics, and select the model that provides best numerical performances in terms of the prediction accuracy of the test set (e.g., F1 score, Area under the curve (AUC) of a receiver operating characteristic (ROC), balanced accuracy, and positive-predictive value (PPV)). Next, we exploit the full data set (without splitting) to train the final model which is to be used to generate prognostic scores for both treated and potential control participants. We will repeat the primary analysis using the double-score-matched study participants and controls. An R-package “dsmatch” will be used to perform matching and assess treatment efficacy after calculating propensity and prognostic scores.

5.8.3 Handling of missing data or dropouts

Other potential sources of bias are missing data, selection bias, and measurement error. We perform the analyses under the assumption of missing (completely) at random. We exclude the cases with missing features if the number of missing subjects is less than 5% of total sample size. Otherwise, we impute values using multivariate imputation by chained equations (MICE) algorithm (Van Buuren, 2018).

The effect of selection bias will be attenuated by appropriately selecting control subjects (who to be matched to treated) from a large pool of patients who are clinically COVID symptomatic.

Systematic bias arising from socio-economic factors will be mitigated by adjusting for various demographic, economic, and societal variables. Measurement errors if there are any, would be considered as random noises, and will be negligible.

